24.0 Appendix

25.0 Statistical Analysis Plan

25.1 Power/Sample Sizes

The sample sizes were chosen based on statistical, analytic, and theoretical considerations. For comparisons of the ABC vs. TAU controls on our outcome variables for Aim 1 (e.g., sun protection behaviors), our N should be able to detect effect sizes that correspond to small effects, Cohen's d = .2 or eta squares of 2%. The effect sizes are based on our pilot study examining patients' sunscreen use intentions following exposure to the ABC intervention (see preliminary studies section) and our studies examining group differences using motivational enhanced interventions to reduce tanning intentions and behaviors. Using power estimation procedures described in Cohen, the sample sizes should vield power of greater than 0.90 for the contrasts of interest. A second analysis that we will pursue will be moderated multiple linear regression or SEM models for Aim 2. [name] has special expertise in such analyses, where we test for effectiveness of the intervention as a function of a moderator variable at baseline (e.g., gender). With every moderator, our sample sizes for each group are reduced by approximately 50%. With our target N = 300 (at baseline), we will have sufficient samples to explore the potential of 2 moderators simultaneously and still have sample sizes that approximate n = 37 per group. Such Ns will also permit us to detect partial r2 sizes in the .04-.06 range and will have power of .70 or greater for the contrasts of interest.

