25.2 General Analytic Issues

Missing Data. We will first test if the data are missing at random by forming a dummy variable that indicates the presence or absence of missing data on a variable. If the data are missing at random, the correlations with other variables should be trivial. We will use the EM method as implemented in SOLAS or FIML in Amos to impute missing data. If the data are not missing at random, then we will include dummy variables that explicitly model the nature of the missing data.

Outlier Analysis and Response Distributions. Throughout all of our statistical analyses, we will be sensitive to the potential influence of outlier cases and possible biases due to ill-behaved (i.e., nonnormal) distributions. Where necessary, we will use robust analytic techniques. Measurement Error. Many of our variables will be subject to some measurement error that, in turn, can bias our parameter estimates. Where possible, we will pursue analytic strategies that permit us to incorporate an error theory into our parameter estimation methods (structural equation modeling). When multiple indicators of an underlying latent variable are present, the incorporation of an error theory is straightforward. When an error theory cannot be empirically operationalized, we will take care to interpret our data in light of the potential bias that may be present.

Multiple Tests and Evaluation of Study Aims. Some of our analyses will have multiple DVs. We will be sensitive to inflated experiment-wise error and control it with the multivariate F statistic based on Pillais criterion in our MANOVAs or with modified Bonferroni methods based on recommendations of Jaccard, [name], and Kirk.

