25.3 Aim 1: Evaluate efficacy of the ABC intervention

[name] (Co-I) will conduct all outcome analyses in order to avoid any bias. First a 2 (Group: ABC vs. Controls) x 3 (Time: baseline, 3 & 6 mo. follow-up) Mixed ANOVA will be conducted to test the intervention on a given outcome variable (e.g., use of sun protection). First, we expect to observe a main effect of Group with the highest reports of sun protection (and lowest reports of UV risk behaviors) occurring in our ABC condition. Second, we anticipate observing a Group x Time interaction with no differences between the groups at baseline but differences (lower risk in the ABC group) at each of the follow-ups. He will also assess the scientific and clinical significance of the effects utilizing the magnitude estimation approach described by Jaccard. Specifically, statistical significance refers to the case when the null hypothesis is rejected, whereas magnitude estimation approaches emphasize the size of the effect. To utilize magnitude

estimation approaches, the researcher must specify an a priori effect size that differentiates a trivial effect from a meaningful effect. If the effect size observed is less than the criterion for meaningfulness, then the result is deemed nonsignificant, even if the null is rejected. We will use Cohen's d statistic to assess clinical significance of the main effects and interactions. We will define an effect as clinically and statistically significant to the extent that the d is greater than or equal to .20.

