25.4 Aim 2: Evaluate moderators and mediators

We will also undertake a set of analyses that identify individual differences in intervention efficacy to examine for whom the intervention is more or less effective. Where the moderator variable is qualitative (e.g., gender), it will be included as another factor into the Mixed ANOVA described earlier. For example, a 2 x 3 x 2 (group x time x patient gender) on sun protection may be used to evaluate gender of the patient as a moderator. First, we will explore whether our effect of Group, where the lowest reports of UV risk behaviors occurring in our ABC condition, differs by the gender of the patient (a group x gender interaction). Second, we will explore whether our Group x Time interaction differs by gender (e.g., a significant group x time x gender interaction). These analyses will be repeated for each of the qualitative moderator variables and evaluated for clinical significance. For quantitative (ordinal or interval) moderator variables (e.g., age), we will calculate product terms between the moderator and group and then analyze the data using moderated regression following the logic in Jaccard & [name]. For mediation, we will use the joint significance test, which Monte Carlo simulations have shown has the most power and lowest Type I error rates relative to other approaches. We will evaluate model fit using global fit indices (e.g., CFI, RMSEA), and more focused indices that suggest specific areas of poor fit (modification indices). We will use bootstrapping where necessary to account for non-normal variable distributions. Using Amos 20.0, if both the a and b paths are significant at the .05 level there is evidence for mediation. The mediated effect is the product of a and b and provides an estimate of the strength of the mediated effect. When there is evidence of mediation, 95% confidence intervals using the bootstrap procedures in Amos can be calculated to provide a range of estimates for the mediated effect. If the confidence intervals do not contain zero there is evidence of statistically significant mediation. Figure 1.

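### The closing sentence of SAP 25.3 makes an observed d of .20 enough for statistical significance, against the section's own definition; the context suggests an added hurdle was meant, so this is a minor wording correction plus a missing definition of d

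*Combined protocol and SAP*

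**What the plan says.** Section 25.3 plans a 2 (group) x 3 (time) mixed ANOVA for each outcome and adds an assessment of scientific and clinical significance by magnitude estimation. It makes four statements that bear on this point, in this order:

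- On tests: "statistical significance refers to the case when the null hypothesis is rejected".
- On the size criterion: "If the effect size observed is less than the criterion for meaningfulness, then the result is deemed nonsignificant, even if the null is rejected".
- On the role of Cohen's d: it is the "statistic to assess clinical significance of the main effects and interactions".
- The rule itself: the team will "define an effect as clinically and statistically significant to the extent that the d is greater than or equal to .20".

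Section 25.2 handles multiple outcomes through tests: the plan will "control it with the multivariate F statistic based on Pillais criterion in our MANOVAs or with modified Bonferroni methods". No alpha is given for Aim 1. The only one in the SAP is in 25.4, for mediation: "if both the a and b paths are significant at the .05 level there is evidence for mediation". Section 25.4 also carries the size criterion to the moderator analyses, which are "repeated for each of the qualitative moderator variables and evaluated for clinical significance".

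**The concern.** The first three statements make d of at least .20 necessary in addition to a rejected null. The closing sentence makes it sufficient, and the word for statistical significance is part of the label it confers. An analyst who applies that sentence as written can call a result with p above .05 statistically significant. The multiplicity control in 25.2 then plays no part in the label, because it acts on tests and the closing sentence contains none.

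The threshold is also not fully defined. It is applied to main effects and interactions of a design with three time points, but the SAP does not name the contrast, the time point or the standardising SD. Nor does it say how d is formed for a Group x Time interaction with 2 degrees of freedom. The sign is open too: 25.3 expects higher sun protection but lower UV risk behaviour in the ABC group, so a benefit on the risk outcomes would be a negative d unless a sign convention is set.

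At stake is which Aim 1 results may be reported as significant.

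**Working it through.** The plan gives no error rate for this rule, so there is no figure of its own to reproduce. The check asks when the closing sentence and the section's definition label the same result differently.

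**Inputs.** Threshold d = .20 (25.3). N = 227, the intended enrolment (protocol 9.1 and 16.0), and N = 300, the SAP target (25.1); both are shown because the documents give both. Assumptions: equal groups, complete data, independent patients, two-sided alpha .05, and within-person correlation rho of .3, .5 or .7 (the documents give none). Results are given as N = 227 / N = 300.

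**(a) Two groups at one visit.** SE(d) = sqrt(4/N) = .1327 / .1155.

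- Smallest d with p < .05: t(.975, N-2) x SE = .262 / .227. An observed d between .20 and these values meets the closing sentence but does not reject the null.
- Example: d = .22 gives t = .22/.1327 = 1.66 and p = .099 at N = 227; at N = 300, t = .22/.1155 = 1.91 and p = .058.
- With no true effect: t = .20/SE = 1.507 / 1.732. In the expected direction the chance is 6.7% / 4.2%. In either direction it is 13.3% / 8.4%.

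This is the simplest case. It is not itself one of the ANOVA effects to which 25.3 assigns d, so those follow.

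**(b) Group main effect, mean of three visits, single-visit SD.** SE = sqrt(4/N) x sqrt((1 + 2 rho)/3).

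**(c) Change from baseline to one visit, single-visit SD.** SE = sqrt(4/N) x sqrt(2(1 - rho)).

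Chance of d at or beyond .20 in either direction with no true effect, 2 x (1 - Phi(.20/SE)):

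| | rho .3 | rho .5 | rho .7 |
|---|---|---|---|
| (b) N = 227 | 3.9% | 6.5% | 9.2% |
| (b) N = 300 | 1.8% | 3.4% | 5.3% |
| (c) N = 227 | 20.3% | 13.2% | 5.2% |
| (c) N = 300 | 14.3% | 8.3% | 2.5% |

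Using the t distribution changes these by less than 0.2 percentage points.

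**(d) Group x Time, 2 df, taking d = 2f (an assumption; sphericity also assumed).** With error df 2(N-2), f² = 2F / (2(N-2)) = F/(N-2). At d = .20, f = .10 and F = .01 x (N-2) = 2.25 / 2.98. P(F(2, 2(N-2)) at or above that) = 10.7% / 5.2%. The smallest d with p < .05 is .232 / .201.

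**Reading the results.** Where a rate is above 5%, the literal rule is looser than the test; where it is below 5%, it is stricter. It is stricter for (b) at N = 227 with rho .3, for (b) at N = 300 with rho .3 or .5, and for (c) at N = 300 with rho .7. Across the definitions tried, the either-direction rate runs from about 2% to 20%. That spread comes from N, from rho and from how d is formed.

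**Added-hurdle reading.** If an effect must both reject the null and reach d of .20, the chance of a false label cannot exceed that of the test alone, so it is at most 5% for a single test.

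**The case against.** The strongest case on the other side is that the paragraph, read as a whole, is clear enough. A test is planned, statistical significance is defined by it, a small effect is ruled out despite a rejected null, and d is assigned to clinical significance. The closing label can then be read as the name for an effect that passes both conditions. This stands in part: the added hurdle is the more likely intention. It does not remove the conflict, because the sentence that states the rule omits the test and uses the word that the section reserved for rejecting the null.

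Three stronger readings are tempting, and the documents do not support them.

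- A reader might infer that Aim 1 is to be judged without any test. The mixed ANOVA in 25.3 and the multiplicity methods in 25.2 are tests, and the plan keeps them.
- A reader might infer that the false-positive rate is 13%. That figure needs the literal reading, N = 227, a single-visit contrast and both directions counted. The sentence is written without an absolute value, and in the expected direction the rate is 6.7%, or 4.2% at N = 300. For the ANOVA effects it can fall below 5%.
- A reader might infer that requiring both conditions undercuts the power stated in 25.1. For the single-visit contrast the smallest significant d (.262 / .227) already exceeds .20, so the size condition removes nothing that the test would have kept. Whether the stated power can be reached is a separate question, and no change to 25.1 follows from this point.

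It is also fair to say that the study describes itself as preliminary (1.1) and is not randomised (7.1), so less rests on the label than in a confirmatory trial. The magnitude method is attributed to an outside source that may specify how d is computed; the SAP itself does not.

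**Conclusion.** The point holds as an internal contradiction in the decision rule of 25.3, together with an incomplete definition of d. It does not show an analysis planned without a test. Under the meaning that the context favours, type I error for a single test is at most 5%. Under the literal sentence, single-visit results with d from .20 to about .26 (N = 227) or .23 (N = 300) would be mislabelled. The no-effect rate for that contrast is 6.7% / 4.2% in the expected direction and 13% / 8% in either. For the ANOVA effects the either-direction rates are 4% to 9% / 2% to 5% (Group main effect, rho .3 to .7) and 10.7% / 5.2% (Group x Time with d as 2f).

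The contradiction rests on the text alone. The rates rest on the assumed two-sided .05, equal groups, complete data, the assumed correlations and the assumed forms of d. Severity: minor.

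**What to change.** Replace the closing sentence of 25.3 with:

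> An effect is statistically significant if the null hypothesis is rejected at two-sided alpha .05 after the multiplicity adjustment in 25.2. It is clinically significant only if, in addition, Cohen's d is at least .20 in absolute value. d is reported with its 95% CI.

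Reword the earlier sentence on effects below the criterion so that it agrees:

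> If the observed effect is smaller than the criterion, the result is not clinically significant, whether or not the null hypothesis is rejected.

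Then state, for each main effect and interaction, the contrast, the time point and the standardising SD used for d, including how the 2-df Group x Time effect is summarised. In 25.4, refer to the same rule and state how d is computed for the moderator interactions. Keep the prespecified .20 criterion.

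Cost: SAP wording only, with no change to data collection or sample size. The downside is that results with d of at least .20 but p above .05 can no longer be called statistically significant.

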25.4 Aim 2: Evaluate moderators and mediators

We will also undertake a set of analyses that identify individual differences in intervention efficacy to examine for whom the intervention is more or less effective. Where the moderator variable is qualitative (e.g., gender), it will be included as another factor into the Mixed ANOVA described earlier. For example, a 2 x 3 x 2 (group x time x patient gender) on sun protection may be used to evaluate gender of the patient as a moderator. First, we will explore whether our effect of Group, where the lowest reports of UV risk behaviors occurring in our ABC condition, differs by the gender of the patient (a group x gender interaction). Second, we will explore whether our Group x Time interaction differs by gender (e.g., a significant group x time x gender interaction). These analyses will be repeated for each of the qualitative moderator variables and evaluated for clinical significance. For quantitative (ordinal or interval) moderator variables (e.g., age), we will calculate product terms between the moderator and group and then analyze the data using moderated regression following the logic in Jaccard & [name]. For mediation, we will use the joint significance test, which Monte Carlo simulations have shown has the most power and lowest Type I error rates relative to other approaches. We will evaluate model fit using global fit indices (e.g., CFI, RMSEA), and more focused indices that suggest specific areas of poor fit (modification indices). We will use bootstrapping where necessary to account for non-normal variable distributions. Using Amos 20.0, if both the a and b paths are significant at the .05 level there is evidence for mediation. The mediated effect is the product of a and b and provides an estimate of the strength of the mediated effect. When there is evidence of mediation, 95% confidence intervals using the bootstrap procedures in Amos can be calculated to provide a range of estimates for the mediated effect. If the confidence intervals do not contain zero there is evidence of statistically significant mediation. Figure 1.
